12.2 Incomplete Follow-up and Missing Data

In the event that a subject does not complete the full study period, the complete set of data available for that subject prior to loss-to-follow-up will be used for analysis. No imputation of missing data will be performed.

12.3 Multi-Center and Multiple Comparison/Multiplicity Adjustments

Data collected from all study sites will be combined and analyzed as a whole. No multi-center adjustments will be made.

12.4 Sample Size and Power

A sample size of [REDACTED] end-users was chosen to attain a margin of error of approximately [REDACTED]. Assuming a [REDACTED] dropout rate, up to [REDACTED] end users will be enrolled to reach a target final sample size of up to [REDACTED]

13.0 STATISTICAL ANALYSES

13.1 Primary and Secondary Objective

Study data collected will be analyzed using appropriate statistical methods as defined by the variable's data level (i.e. continuous, ordinal, categorical, etc.). This includes but is not limited to frequency and percentages for categorical measures and mean [standard deviations] for continuous measures. [REDACTED]

13.2 Interim Analyses

An interim analysis is planned for when one of the following milestones occur, whichever occurs first: 1) [REDACTED] subjects have provided product assessment data via the end of study questionnaire or 2) the study reaches [REDACTED]. All subject data that has been gathered and released [REDACTED] on or prior to this milestone will be included in the interim analysis. [REDACTED]

[REDACTED] Any amendments will be documented per Section 17.0.

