7.0 STUDY DESIGN

The study will be executed at a [REDACTED], and will not require [REDACTED]

[REDACTED] Subjects will be assigned to one of two possible study Groups. Group 1 will include subjects who currently use [REDACTED] IC products. Group 2 will include subjects who currently do not use [REDACTED] IC products but do use [REDACTED]. Subjects will be assigned either to Group 1 or Group 2 depending on their current hydrophilic IC product usage at time of completing the eligibility screener.

Subjects in Group 1 will be shipped [REDACTED] to use over a consecutive [REDACTED]. Subjects will be instructed to use Study Catheter [REDACTED] according to their usual care practices. After each day, subjects will complete a daily check-in to confirm the number of ICs they have remaining and if there have been changes in their overall health. Once the subject uses all of 30 study catheter [REDACTED] or [REDACTED] have elapsed, whichever occurs first, the subject will complete an end-of-study questionnaire about their overall experience.

Subjects in Group 2 will be shipped [REDACTED] IC [REDACTED]
[REDACTED] Subjects will first sample the currently marketed product for a [REDACTED], or until they use a maximum of 60 Study Catheter [REDACTED] whichever occurs first (“sampling period”). After the sampling period, subjects will switch to using Study Catheter [REDACTED] Subjects will use the study Catheter [REDACTED] for a consecutive [REDACTED], or until they have used all 30 Study Catheter [REDACTED] whichever occurs first. Subjects will be instructed to use both study catheters according to their usual care practices. After each day, subjects will complete a daily check-in to confirm the number of ICs they have remaining and if there have been changes in their overall health. After using both study catheters, the subjects in Group 2 will complete an end-of-study questionnaire about their overall experience.

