9.4 Method of Assigning Subjects to Study Groups

All subjects will be assigned to one of two possible study Groups. Group 1 will include subjects who currently use [REDACTED] IC products. Group 2 will include subjects who currently do not use [REDACTED] IC products but do use a different type of [REDACTED] IC on the market, as defined in the eligibility criteria in Sections 8.1 and 8.2. Subjects will be assigned either to Group 1 or Group 2 depending on their current IC product reported at time of completing the eligibility screener.

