12.0 STATISTICAL METHODS

12.1 Analysis Principles

Enrolled subjects who provide product assessment data will be eligible for analysis; subjects who screen fail or did not provide any study product assessment data will be excluded from analysis.

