15.0 FINAL REPORT

The Sponsor will write and issue an interim report per the schedule provided in Section 13.2 and a final report at study completion. It is the responsibility of the Investigator to provide the interim and final reports to the IRB, as required. In the event that the target sample size is enrolled and available for analysis by the time of the planned interim analysis, a final report will be issued in lieu of an interim report and a note to file will be created to document this event.

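### Does an interim cut by questionnaire count over-represent Group 1 badly enough to need a change in Section 13.2?

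*Combined protocol and SAP*

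**What the plan says.** Section 7.0 gives the two groups different routes to the same questionnaire. Group 1 completes it "Once the subject uses all of 30 study catheter", or when a redacted time limit passes if that is sooner. Group 2 first samples the marketed product for a redacted period "or until they use a maximum of 60 Study Catheter", whichever is sooner, and then uses up to 30 study catheters, again with a redacted time limit. The section adds: "After using both study catheters, the subjects in Group 2 will complete an end-of-study questionnaire about their overall experience".

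Under Section 9.4 the groups are not randomised. Subjects are placed "depending on their current IC product reported at time of completing the eligibility screener". The visible text gives no quota or ratio.

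Section 13.2 sets the interim at the earlier of two milestones. The first is reached when a redacted number of "subjects have provided product assessment data via the end of study questionnaire"; the second is redacted. Data gathered and released "on or prior to this milestone will be included in the interim analysis". Further text in 13.2 is redacted, as is the end of 13.1, whose visible part plans descriptive summaries only.

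Section 12.1 defines who is analysed: "Enrolled subjects who provide product assessment data will be eligible for analysis". Section 12.3 pools data across study sites and is silent on pooling Groups 1 and 2. Section 15.0 adds that if the target sample is already enrolled and available by then, "a final report will be issued in lieu of an interim report".

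**The concern.** A trigger that counts completed questionnaires favours subjects who finish quickly. Group 1 has one period to complete and Group 2 has two, so while subjects are still in progress the completers would tend to include too many from Group 1.

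The groups are defined by the product they already use, so their opinions of the study catheter could differ. A single all-subject acceptability percentage at the interim would then partly reflect which group finished first, and it could move by the final report with nobody's opinion changing. The investigator passes the interim report to the IRB as required (Section 15.0), so such a figure would have readers.

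**Working it through.** The documents give no figure to reproduce, because sample size, margin of error, dropout, milestones and period lengths are all redacted. The check below establishes the direction and then the plausible size.

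**From the documents (Section 7.0).** Catheters used before the questionnaire: Group 1, at most 30; Group 2, at most 60 + 30 = 90.

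**Assumed.** N = 100 subjects; enrolled Group 1 share p = 0.5; steady enrolment over A = 30, 60 or 90 days; 4 to 6 catheters a day (uniform); no time limit binding; no dropout; one all-subject count k as trigger; 80% acceptability; a 15-point difference between groups.

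**Step 1: lag.** The mean sampling period is S = 60 × ln(6/4)/2 = 12.2 days. Subjects enrolled during one such period number m = S × N/A = 40.5, 20.3 and 13.5 for the three enrolment lengths.

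**Step 2: Group 1 share at the cut.** With Group 1 completers pN(t − L)/A and Group 2 completers (1 − p)N(t − L − S)/A, where t is the cut date and L the evaluation period, the Group 1 share is p + p(1 − p)m/k. This holds only while completers still come from open enrolment and k is at least p × m. Outside that range it fails: p = 0.7, k = 25, m = 40.5 gives 0.7 + 0.21 × 40.5/25 = 104%, which is impossible.

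**Step 3: shift in a pooled percentage.** Shift = 15 × (share − 0.5). Sampling margin = 1.96 × √(0.8 × 0.2/k).

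| k | Group 1 share (A = 30 / 60 / 90) | Shift, points | Margin, points |
|---|---|---|---|
| 50 | 70.3 / 60.1 / 56.8% | 3.0 / 1.5 / 1.0 | 11.1 |
| 25 | 90.5 / 70.3 / 63.5% | 6.1 / 3.0 / 2.0 | 15.7 |

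Simulation under the same assumptions gives 70.6 / 60.0 / 56.8% at k = 50 and 89.1 / 70.2 / 63.6% at k = 25. At k = 100 everyone has finished and the share is 50%.

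**Step 4: a different lag.** If a time limit capped sampling at 7 days (assumed), m = 7 × 100/A = 23.3, 11.7 and 7.8. The shares at k = 50 are then 62 / 56 / 54% and the shifts 1.8 / 0.9 / 0.6 points. If use were 3 a day with no cap, S = 20 days and m = 66.7, 33.3 and 22.2. The shares become 83 / 67 / 61% and the shifts 5.0 / 2.5 / 1.7 points.

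**Step 5: ceiling.** Even an interim made up wholly of Group 1 shifts a 50:50 pooled figure by only 0.5 × 15 = 7.5 points. At a 70.3% share and k = 50, the groups would have to differ by 11.1/0.2025 = 55 points before the shift reached the sampling margin.

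**Cross-check by calendar day.** At 4 catheters a day the questionnaire falls at 30/4 = 7.5 days for Group 1 and 90/4 = 22.5 days for Group 2. With 50:50 enrolment still open at day T, the Group 2 share of completers is (T − 22.5)/[(T − 7.5) + (T − 22.5)]: 25% at day 30, 42% at day 60, 45% at day 90 and 48% at day 180. The direction is the same, and the gap closes as enrolment lengthens.

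**The case for a change.** The best case for acting is that the mechanism is in the visible text, two different models agree on its direction, and the remedy is cheap: one sentence asking for interim results by group, with no data lost. A systematic shift is also not excused by being smaller than random error, since it is avoidable. Nor does it require enrolment to be open; it can persist after enrolment closes, until the last Group 2 subjects finish.

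The mechanism and its direction stand. The need for a change does not. Harm requires all of the following: subjects still in progress at the cut, no substitution of a final report under Section 15.0, Group 2 not enrolled earlier, a trigger not set by group, a single pooled figure, and groups that answer differently. The documents settle none of these. The redaction before the word for subjects in 13.2 could hide a group qualifier as well as a number, and the second milestone may come first. By-group presentation may be specified in the redacted parts of 13.1 or 13.2, and text hidden by redaction cannot be counted as absent.

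The enrolled mix is also not a visible target. Section 9.4 lets it follow from whoever enrols, so even a final pooled figure would carry a mix that the visible text does not fix.

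**Conclusion.** No change to the plan follows. Group 2's later questionnaire can tilt an early interim towards Group 1, but no visible rule turns that into a wrong result: the visible summaries are descriptive, and no test or decision is seen to rest on the interim. The final analysis is unaffected provided all subjects are followed up. The plan already separates the groups in definition, eligibility and schedule, so showing interim results by group with counts is what an analyst would ordinarily do. That display would change no estimate within either group.

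Under the stated assumptions the effect on a pooled figure is about 1 to 3 points at 50 questionnaires and 2 to 6 at 25, against sampling margins of 11.1 and 15.7. A binding time limit on sampling would make it smaller; slower catheter use, faster enrolment or a larger group difference would make it larger. These figures are illustrative, since every quantity that would fix the true size is redacted. The sponsor can confirm from the unredacted text that interim results are shown by group, but this is a question about presentation and not a defect.

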14.0 STUDY DOCUMENTATION AND RECORD KEEPING

The Sponsor and clinical site are required to retain essential study documents within a study TMF. The Sponsor is responsible to retain study documentation per the retention schedule set forth in [REDACTED] Clinical sites other than Hollister Incorporated are required to retain study documentation for [REDACTED] following Sponsor notification of study closure.

15.0 FINAL REPORT

The Sponsor will write and issue an interim report per the schedule provided in Section 13.2 and a final report at study completion. It is the responsibility of the Investigator to provide the interim and final reports to the IRB, as required. In the event that the target sample size is enrolled and available for analysis by the time of the planned interim analysis, a final report will be issued in lieu of an interim report and a note to file will be created to document this event.

16.0 MONITORING

[figure not shown]
A qualified Hollister Incorporated monitor or designee will monitor the study data to verify that forms are completed, and that the conduct of the trial is in compliance with the currently approved protocol/ amendment(s) procedures, GCP, and any applicable regulatory requirements.

All data collected for this study is subject self-report data via ePRO questionnaire, and therefore there will be no source documents for monitoring. To the best of the Sponsor's ability, data logic and validation checks will be configured in the EDC ePRO module so that subjects will receive warning messages at time of entry about inconsistent or invalid entries, in order to assure quality and completeness of data. Since the study collects [REDACTED] there will be minimal corrections or modifications by the Sponsor to ePRO data. Any modification of ePRO data will only be done following direct contact and clarification from the subject. There will be no modification to any data capturing subject opinion or assessment of study product. The Sponsor may contact subjects to clarify factual data, such as date of first study product application, or any unclear responses on the ICF and the Eligibility Screener, to assure proper and full consent of subjects, as well as confirmation of eligibility before study enrollment. The Sponsor will contact any subject who directly reports or implies a change in their health status, in order to assure subject safety while using the study product.

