5.0 STUDY OBJECTIVES

5.1 Primary Objective

The primary objective of this study is to assess [REDACTED] hydrophilic [REDACTED] technology used on the study product. Assessment data will be collected to determine whether end users find the [REDACTED] hydrophilic [REDACTED] technology to be [REDACTED] acceptable [REDACTED]
[REDACTED]
[REDACTED] Product safety will also be monitored through daily questionnaires intended to track adverse events.

[figure not shown]

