10.1 Handling Adverse Events

Upon study enrollment, all subjects are informed to notify the Investigator immediately if they experience any health or study-related problems. Subjects will be asked daily to report any change in their health status during the course of the study on the Daily Questionnaires [REDACTED]. The PI or designee will contact the subject if clarification of the information reported on the daily form is needed. The PI will determine if an AE has occurred, the severity of the AE, and if it was related to the study product. AEs will be documented on [REDACTED] in the EDC system. Subjects who report AEs may be directed to seek care from their healthcare provider or emergency room, as appropriate.

All AEs are followed to determine resolution for up to [REDACTED] by the Investigator and the Adverse Event Form is updated to indicate date of resolution. If at any point, the Investigator determines the subject should no longer remain on the study product, the subject should be discontinued from the study.

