11.0 DATA MANAGEMENT

It is the responsibility of the Investigator to ensure the completeness and accuracy of all study data collected in the EDC system. Subject name and contact information will be treated as Protected Health Information and not included in any dataset for analysis. All datasets for study analysis will include only de-identified data.

The electronic ICF and electronic case report forms (eCRFS) will be collected directly from research subjects using a secure, cloud-based EDC and electronic patient reported outcomes (ePRO) system [REDACTED]. [REDACTED] will be configured by the Sponsor Data Manager for study-specific data capture. Study forms such as the Adverse Event Form, Protocol Deviation Form, and Contact Log will be entered by the study personnel at the site.

Subjects will be provided with a link to the EDC/ePRO system via an email, as each study form is made available to them to complete. Subjects will set up their own, secure password to the system and that password remains unknown to the Sponsor. The [REDACTED] EDC will provide an audit log that verifies that all ePRO data were entered by the subjects themselves. The audit log will also document when and by whom any modifications were made to the data after initial entry.

To the best of the Sponsor's ability, data logic and validation checks will be configured in the ePRO system so that subjects will receive warning messages at time of entry regarding inconsistent or invalid entries, in order to assure quality and completeness of data. Because the study collects self-report data directly from the study participants, there will be minimal corrections or modifications by the Sponsor to ePRO data. Any modification of any ePRO data will only be done following direct contact and clarification from the research subject. There will be no modification to any data capturing subject opinion or assessment of study product. The Sponsor may contact the subject to clarify factual data, such as date of first study product use, or any unclear responses on the ICF and the Eligibility Screener, to assure proper and full consent of subjects, as well as confirmation of eligibility before study

enrollment. The Sponsor will contact any subject who directly reports or implies a change in their health status, in order to assure subject safety while using the study product.

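### Does the statement that there are no source documents leave the staff-entered adverse event records unchecked?

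*Combined protocol and SAP*

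**What the plan says.** Section 5.1 places safety within the primary objective: "Product safety will also be monitored through daily questionnaires intended to track adverse events".

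Section 10.1 describes how a report becomes an AE record. At enrolment, "all subjects are informed to notify the Investigator immediately if they experience any health or study-related problems". Subjects are also asked every day about changes in health. Then: "The PI or designee will contact the subject if clarification of the information reported on the daily form is needed". The decision follows: "The PI will determine if an AE has occurred, the severity of the AE, and if it was related to the study product". AEs are documented in the EDC system and followed for resolution.

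Section 11.0 says who enters what. Subjects complete their own questionnaires, but "Study forms such as the Adverse Event Form, Protocol Deviation Form, and Contact Log will be entered by the study personnel at the site". It also commits to follow-up: "The Sponsor will contact any subject who directly reports or implies a change in their health status, in order to assure subject safety". Section 16.0 repeats that commitment. Section 11.0 further makes the Investigator responsible for complete and accurate EDC data, provides an audit log of changes, and has the Investigator sign all EDC data before export and analysis.

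Section 16.0 gives the sponsor's monitor this task: "will monitor the study data to verify that forms are completed, and that the conduct of the trial is in compliance with". The standards it then names are the approved protocol, GCP and applicable regulations. Its next paragraph opens: "All data collected for this study is subject self-report data via ePRO questionnaire, and therefore there will be no source documents for monitoring".

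**The concern.** The sentence in Section 16.0 rests on a premise that the protocol contradicts. A questionnaire answer typed in by the subject is its own source, so nothing separate exists to verify it against. An AE Form is different. Staff write it after a PI judgement, and an earlier record usually lies behind it: the daily questionnaire or the subject's direct notification. For that form the conclusion about source documents does not follow.

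The worry is practical. The section that instructs the monitor appears to say there is nothing to compare. A reported health change that never led to an AE decision, or an AE Form that disagrees with the subject's report, might then pass unnoticed into the interim and final reports. The PI is a sponsor employee, the sponsor acts as the clinical site (Section 3.0), and the study is open label (Section 9.5). A traceable link from report to decision is therefore a reasonable thing to look for, and no visible passage names a step that matches the two records.

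**Working it through.** The plan gives no figure on this point, so there is nothing to reproduce. The check sets the passages side by side and asks whether a reported health change can be lost if the plan is followed as written.

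1. **Is the premise true?** No. Section 16.0 speaks of all data. Section 11.0 lists three staff-entered forms, and Section 6.3 adds dispensing and return records entered by research staff or the sponsor. The contradiction is real. Of these records, only the AE Form bears on the safety results.

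2. **What does the sentence govern?** The rest of its paragraph concerns entry checks in the ePRO module, limits on changing ePRO data, and contact with subjects to clarify answers or follow up health changes. In context it explains why subject-entered answers have no separate source. It does not forbid the monitor to read two forms held in the same EDC system.

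3. **Follow one report through the plan.**
   - The subject gives a positive daily answer or notifies the Investigator directly (10.1).
   - The sponsor contacts any subject who reports or implies a health change (11.0, 16.0). This carries no condition. The conditional contact in 10.1 is an additional one for clarification, and the two can coexist. The PI and study team are sponsor employees, so the same organisation makes both contacts.
   - The PI decides on occurrence, severity and relatedness, and AEs are documented in the EDC system (10.1).
   - The Investigator is responsible for completeness and accuracy, the audit log records later changes, and the Investigator signs before export (11.0).
   - The monitor checks form completion and compliance with the protocol (16.0). The sequence in 10.1 is part of what must be complied with.

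4. **Where could a report be lost?** Only where one of these steps is not carried out. The subject's daily answer would still be in the EDC system, because ePRO data are changed only after contact with the subject and changes are logged. The omission could therefore be traced.

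5. **What would a listing add?** It would match each positive daily answer and each logged health contact with an AE Form or a recorded decision that no AE occurred. It would detect lapses in step 3. It would not alter a definition, an analysis set or an estimate. The sponsor would still do the review, so it would add no independence.

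6. **Can the effect be sized?** No. The sample size, study duration and expected AEs are redacted. Neither the direction nor the size of any error in AE counts can be derived.

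**The case for a change.** The strongest case for a change is that no visible control is actually a comparison. Verifying that forms are completed may miss a form that was never opened. Contact with the subject is stated to serve safety, not to verify the record. The audit log shows who changed an entry, not whether two forms agree. The accuracy duty and the signature rest with the Investigator, while the AE decision is the PI's, so neither is an outside check. The plan also does not say that a decision that no AE occurred is recorded, or that direct notifications are logged; it only names a Contact Log. Against that, one corrected sentence and one listing look cheap.

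Much of this stands as description. The sentence is too broad, the comparison is not named in the visible text, and the checks are internal to the sponsor. Redaction cannot settle whether a matching step exists. Parts of Sections 10.1, 10.3, 11.0 and 16.0 are blacked out and the attachments are not shown. The gap in 16.0 itself probably hides only wording parallel to that of 11.0.

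What does not stand is the step from an unnamed comparison to unsound safety results. The controls have to be read together, and together they require contact, a decision, documentation, sign-off before export and a compliance check. The proposed listing would be equally internal. Its cost is also more than a wording change: Section 17.0 requires PI review and IRB approval of any amendment, and a recorded negative decision for each unmatched line would be a new record that the visible text does not call for.

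**Conclusion.** The inconsistency is genuine but amounts to a wording slip. If Sections 10.1, 11.0 and 16.0 are followed as written, each reported health change leads to follow-up and a PI determination, and AEs are documented before the Investigator signs and the data are exported. The safety results remain sound under the plan as it stands. The visible analysis in Section 13.1 is descriptive, and no result is shown to change.

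A reconciliation listing is an optional quality check that the monitor can run under the existing compliance remit. It guards against departures from the plan and does not repair a defect in it. The demonstrated effect on AE counts is nil, and a possible effect cannot be quantified from the documents.

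This conclusion assumes that the monitor reads the sentence on source documents in the context of subject-entered data, and that the unconditional contact commitment in Sections 11.0 and 16.0 is carried out. It does not depend on anything in the redacted text.
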